### **3.2 Number of Sites**

The study will be conducted at approximately 16 sites within the United States. If a site does not enroll subjects within 3 months of site initiation, the site may be closed.

### **3.3 Number of Subjects**

Participants in this clinical investigation shall be referred to as “subjects”.

A total of at least **52** subjects and up to approximately 60 subjects with migraine will be enrolled in Cohorts 1 and 2, with at least **12** subjects and up to approximately 22 subjects enrolled into Cohort 1 (< 40 kg) and at least 35 subjects and up to approximately 38 subjects enrolled into Cohort 2 ( $\geq 40$  kg). The number of subjects enrolled into Cohort 1 and Cohort 2 are considered sufficient in order to collect appropriate PK data and preliminary safety data able to support the initiation of the AMG 334 pediatric Phase 3 safety and efficacy studies. This includes an anticipated rate of early discontinuations up to 20% over the first 12 weeks, which is expected to be similar across the two cohorts.

### **3.4 Replacement of Subjects**

Subjects who are withdrawn or removed from treatment or the study may be replaced by another subject in the same body weight cohort at the discretion of the Amgen Medical Monitor in consultation with the Principal Investigator.

### 3.5 Estimated Study Duration

#### 3.5.1 Study Duration for Subjects

The estimated study duration for subjects completing only the initial 12 week treatment phase is up to 27 weeks, and includes:

- Up to 3 weeks for screening
- 12 week treatment phase
- 12 week safety follow-up phase (16 weeks after the last dose of AMG 334)

The estimated study duration for subjects completing the initial 12 week treatment phase and the optional 40-week extension phase is up to 67 weeks, and includes

- Up to 3 weeks for screening
- 12 week treatment phase
- Optional 40-week extension phase
- 12 week safety follow-up phase (16 weeks after the last dose of AMG 334)

#### 3.5.2 End of Study

**Primary Completion:** The primary completion date is defined as the date when the last subject is assessed or receives an intervention for the final collection of data for the primary endpoint(s), for the purposes of conducting the primary analysis (ie, when the last subject completes the 12 Week assessment or is discontinued from the study).

**End of Study:** The time when the last subject is assessed or receives an intervention for evaluation in the study (ie, when the last subject completes the study, which includes the safety follow-up visit 16 weeks after the last dose of Investigational Product, or is discontinued from the study for other reasons described in Section 8).

If the study concludes prior to the primary completion date originally planned in the protocol (ie, early termination of the study), then the primary completion date will be the date when the last subject is assessed or receives an intervention for evaluation in the study (ie, last subject last visit).

## 4. SUBJECT ELIGIBILITY

Investigators will be expected to maintain pre-screening and screening logs of all potential study candidates which includes limited information about the potential candidate (eg, date of screening).

Before any study-specific activities/procedure, the appropriate written informed consent and subject assent must be obtained. In addition to written informed consent from a

legally acceptable representative, the assent of the child must also be obtained as appropriate to the age of the subject and/or based on local regulations. (see Section 11.1).

#### **4.1 Inclusion Criteria**

101. Subject's legally acceptable representative has provided informed consent and the subject has provided written assent based on local regulations and/or guidelines prior to any study-specific activities/procedures being initiated.
102. Male and female children and adolescents 6 and < 18 years of age at time of consent
103. Body weight  $\geq$  18 kg upon entry into screening
104. History of migraines, with or without aura, according to the ICHD-III for at least 12 months prior to the study screening
105. Frequency of  $\geq$  4 migraine days per month in each of the 3 months prior to the study screening period
106. Physical and neurological examinations, clinical laboratory values, and 12-lead ECGs are clinically acceptable to the investigator and Amgen medical monitor at screening

#### **4.2 Exclusion Criteria**

201. Currently receiving treatment in another investigational device or drug study, or less than 30 days (small molecules), 90 days (biologic agents), or 5 half-lives (whichever is longer) since ending treatment on another investigational device or drug study(s). Other investigational procedures while participating in this study are excluded.
202. Use of more than 2 migraine prophylactic medications within 1 month prior to Study Day 1 (see Section 6.4).
203. Taken opioid or butalbital-containing analgesics on  $\geq$  4 days per month for any indication in either month during the 2 months prior to screening
204. History of migraine with brainstem aura or hemiplegic migraine headache
205. Medical history or other condition that compromises the ability of the subject or legally acceptable representative to give appropriate informed consent and/or assent
206. Malignancy except non-melanoma skin cancers or cervical cancer in situ within the last 5 years.
207. History of hypertension

208. History of chronic or frequent clinically significant painful condition other than migraine
209. History of chronic anemia
210. Uncontrolled asthma or uncontrolled diabetes
211. Vaccinations within 1 month of Study Day 1
212. Major surgery within 6 months of Study Day 1
213. Hospitalization > 24 hours within 28 days of Study Day 1
214. Abnormal hepatic function: ALT or AST  $\geq$  2.0 times the upper limit of normal (ULN) for the age range, confirmed by repeated measure
215. Abnormal renal function: creatinine  $\geq$  1.5 times the ULN for the age range, confirmed by repeated measure
216. Known positive results for Human Immunodeficiency Virus (HIV)
217. Positive Hepatitis B Surface Antigen (HepBsAg), Hepatitis B Core Antibody (HepBc Ab) (indicative of chronic Hepatitis B) or detectable hepatitis C virus Ribonucleic acid (RNA) by Polymerase Chain Reaction (PCR) (indicative of active Hepatitis C – screening is generally done by Hepatitis C Antibody (HepCAb), followed by hepatitis C virus RNA by PCR if HepCAb is positive)
218. Subject has known hypersensitivity or known allergy to any of the products to be administered during dosing
219. Subject likely to not be available to complete all protocol-required study visits or procedures, and/or to comply with all required study procedures to the best of the subject and investigator's knowledge
220. Subject was previously enrolled in this study
221. Females of reproductive potential who are unwilling to practice an acceptable method(s) of effective birth control while on study through 16 weeks after receiving the last dose of study drug. Acceptable methods of effective birth control includes sexual abstinence (male, female), hormonal birth control, or intrauterine devices (IUDs). Barrier methods are acceptable if a condom with spermicide (male) is used in combination with diaphragm, cervical cap, or cervical sponge (female).  
Reproductive potential is defined as a female who has had at least one menstrual period, regardless of age
222. Female who is breastfeeding or who plans to breastfeed while on study through 16 weeks after receiving the last dose of study drug

- 223. Female of reproductive potential with a positive pregnancy test. Reproductive potential is defined as a female who has had at least one menstrual period, regardless of age
- 224. Female subject planning to become pregnant during study through 16 weeks after receiving the last dose of study drug
- 225. Male subjects with pregnant partners or whose partners plan to become pregnant during the study
- 226. Positive illicit drug and/or alcohol test at screening
- 227. Known substance abuse (eg alcohol, cannabis, illicit drugs) within 12 months of screening
- 228. Inability, or unwillingness, to refrain from alcohol consumption during study participation
- 229. Subject has moderate or severe depression based on: a total score of > 11 on the Patient Health Questionnaire modified for adolescents (PHQ-A) or investigator's clinical judgment for children (Refer to Section [7.2.11](#))
- 230. Subject has a history or evidence of suicidal ideation (endorsing item 4 or 5) or any suicidal behavior based on an assessment with the Columbia Suicide Severity Rating Scale (C-SSRS) at screening or at baseline
- 231. History or evidence of any other clinically significant disorder, condition or disease that, in the opinion of the investigator or Amgen medical monitor, if consulted, would pose a risk to subject safety or interfere with the study evaluation, procedures or completion
- 232. Subject deemed likely to require modification in migraine prophylactic medication during study participation in the opinion of the investigator or Amgen medical monitor

## 5. SUBJECT ENROLLMENT

Enrollment will be staggered by age category with adolescents (ie, subjects 12 to < 18 years of age) starting enrollment first.

Children 6 to < 12 years of age at the time of consent, will participate in the initial treatment phase, for a total of 12 weeks of treatment. Adolescents 12 to < 18 years of age at time of consent will participate in the initial treatment phase for a total of 12 weeks of treatment after which they will have the option of continuing treatment in an optional 40-week extension phase, for a total of 52 weeks of treatment. A safety follow- up visit will take place 16 weeks after the last dose to complete

EOS assessments either (i) after completion of the initial 12 week treatment phase, (ii) after completion of the optional 40-week extension phase for those adolescents who choose to continue treatment or (iii) after the last dose received before discontinuation of treatment during the study.

Before subjects begin participation in any study-specific activities/procedures, Amgen requires a copy of the site's written institutional review board/independent ethics committee (IRB/IEC) approval of the protocol, informed consent form, assent, and all other subject information and/or recruitment material, if applicable. All legally acceptable representatives must personally sign and date the informed consent form before commencement of study-specific procedures. All subjects must provide appropriate assent before commencement of study-specific procedures. Subjects are considered enrolled once the investigator has confirmed they meet all eligibility criteria.

The Investigator is to document the enrollment decision and date, in the subject's medical record and in/on the enrollment eCRF.

Each subject and/or legal representative who signs the informed consent and assent enters into the screening period for the study and receives a unique subject identification number before any study procedures are performed. The subject identification number will be assigned manually. This number will be used to identify the subject throughout the clinical study and must be used on all study documentation related to that subject. Re-screening of subjects is acceptable upon discussion with and approval by the Amgen Medical Monitor.

The unique study identification number will consist of 11 digits. The first 3 digits will represent the last 3 digits of the protocol number (eg, 172). The next 5 digits will represent the country code and site number (eg, 66003) and will be identical for all subjects at the site. The last three digits will be assigned in sequential order as subjects are screened (eg, 001, 002, 003). The subject identification number must remain constant throughout the entire clinical study; it must not be changed after initial assignment, including if a subject is rescreened.

## **5.1 Allocation to Cohort (Initiation of Screening) and Treatment Assignment (Enrollment)**

Subjects will be assigned to one of two cohorts based the subject's body weight on Day 1. Enrollment requirements for subjects in Cohort 1 and Cohort 2 will be tracked and administered via IVRS to ensure that the minimum number of subjects in each

---

cohort is achieved. Requests for initiation of screening procedures will be administered via IVRS.

Randomization will be based on a schedule generated by Amgen before the start of the study and will be centrally executed using the IVRS. Subjects eligible for randomization on Day 1 will receive a unique randomization number, which will be assigned in sequential order in which a subject met eligibility criteria and study staff dialed into IVRS. At no time will the same randomization number be assigned to more than one subject.

Subjects in Cohort 1 (weighing < 40 kg) will be randomized in a 1:2 allocation ratio to low dose (35 mg AMG 334), or high dose (70 mg AMG 334). Subjects in Cohort 2 (weighing  $\geq 40$  kg) will be randomized in a 1:4 allocation ratio to low dose (70 mg AMG 334), or high dose (140 mg AMG334). The treatment dose assigned and treatment assignment date are to be documented in the subject's medical record.

The treatment dose assigned (low-dose or high-dose of the body-weight cohort AMG 334) will be administered in either cohort in an open-label fashion.

## **5.2 Calls to Interactive Voice Response System (IVRS)**

Sites are to call the IVRS for the following: to enter the subject into the initial screening phase and to randomize an eligible subject into the treatment phase.

## **6. TREATMENT PROCEDURES**

### **6.1 Classification of Product(s), Medical Device(s), and/or Combination Product(s)**

The Amgen Investigational Product used in this study is AMG 334.

The Investigational Product Instruction Manual (IPIM), a document external to this protocol, contains detailed information regarding the storage, preparation, destruction, and administration of AMG 334.

### **6.2 Investigational Product**

Investigational Product(s) will be administered at the research facility by a qualified staff member. A physician must be available at the time of administration of Investigational Product.

#### **6.2.1 AMG 334**

AMG 334 will be manufactured and packaged by Amgen Inc. The excipients are appropriate for the use in children, thus obviating the need for development of a separate pediatric formulation. AMG 334 will be packaged in prefilled syringes containing either 1 mL of 70 mg/mL AMG 334 or 1 mL of 140 mg/mL AMG 334.

AMG 334 will also be packaged in 3 mL clear glass vials containing 1 mL of 70 mg/mL AMG 334.

#### **6.2.1.1 Dosage, Administration, and Schedule**

A qualified staff member will administer the appropriate dose and number of AMG 334 injections into the abdomen, the upper arm or the upper thigh, the 3 anatomical sites for administration of Investigational Product. For subjects weighing < 40 kg at baseline (Cohort 1), one injection of either 35 mg (0.5 mL) or 70 mg (1 mL) will be administered. For subjects weighing ≥ 40 kg at baseline (Cohort 2) one injection of either 70 mg (1 mL) or 140 mg (1 mL) will be administered.

Subjects in either cohort will be randomly assigned to one of two Investigational Product dose levels; doses are fixed and will not be adjusted for individual subjects during the study. The anatomical sites for administration of Investigational Product are the upper arm, upper thigh, or abdomen.

All subjects in this study will be administered AMG 334 against a background of allowed concomitant medications, including agents for migraine prevention.

AMG 334 will be administered Q4W on Study Day 1, and on Study Days 29 (± 3 days) and 57 (± 3 days). Adolescent subjects will have the option to participate in the optional 40-week extension phase, receiving IP as noted in the Schedule of Activities ([Table 1](#) and [Table 2](#)), at the dose they received during the initial 12 Week treatment phase regardless of any changes in weight that might occur during the study. All subjects will be monitored on site 2 hours post-dose on Day 1 for any acute reactions that might occur. All subjects will be monitored on site for 30 minutes post-dose on Days 29 and 57. The post-dose safety monitoring will be extended for 2 hours if the subject shows any safety concerns post-dose during the last dosing visit. The date, time, injection location, volume (full, partial, or none), and lot number of each treatment will be recorded in the subject's source documents and on the appropriate eCRF. The effects of overdose of AMG 334 are not known. All overdose occurrences must be documented and corresponding adverse events must be recorded on the appropriate eCRF and in the source documents.

The study may be terminated at any point in time at the discretion of the sponsor. Subjects who permanently discontinue IP during the initial 12 week treatment phase will have the EOS/Week 12 visit assessments performed and will then return for the safety follow-up visit 16 weeks after the last dose of Investigational Product. Subjects who

permanently discontinue IP during the 40-week extension phase will have the EOS/Week 52 visit assessments performed and then will return for the safety follow-up visit 16 weeks after the last dose of Investigational Product.

### **6.2.2 Medical Devices**

The following investigational combination product or medical device provided by Amgen for use in this study is the pre-filled syringe.

The AMG 334 pre-filled syringe is a single-use, disposable, handheld manual injection device for fixed dose SC injection of [1 mL of 70 mg/mL] deliverable volume.

Additional details are provided in the IPIM.

Other non-investigational medical devices may be used in the conduct of this study as part of standard care.

Non-investigational Non-Amgen medical devices (eg, syringes, sterile needles), that are commercially available are not usually provided or reimbursed by Amgen (except, for example, if required by local regulation). The investigator will be responsible for obtaining supplies of these devices.

### **6.3 Hepatotoxicity Stopping and Rechallenge Rules**

Subjects with abnormal hepatic laboratory values (eg, alkaline phosphatase [ALP], aspartate aminotransferase [AST], alanine aminotransferase [ALT], total bilirubin [TBIL] or international normalized ratio [INR]) or signs/symptoms of hepatitis may meet the criteria for discontinuation of Investigational Product depending upon the clinical circumstances discussed below (as specified in the FDA Guidance for Industry Drug-Induced Liver Injury: Premarketing Clinical Evaluation, July 2009).

#### **6.3.1 Criteria for Permanent Withholding of AMG 334 due to Potential Hepatotoxicity**

The following stopping and/or withholding rules apply to subjects for whom another cause of their changes in liver biomarkers (TBL, INR, and transaminases) has not been identified.

Important alternative causes for elevated AST/ALT and/or TBIL values include, but are not limited to:

- Hepatobiliary tract disease
- Viral hepatitis (eg, Hepatitis A/B/C/D/E, Epstein-Barr Virus, cytomegalovirus, Herpes Simplex Virus, Varicella, toxoplasmosis, and Parvovirus)

- Right-sided heart failure, hypotension or any cause of hypoxia to the liver causing ischemia
- Exposure to hepatotoxic agents/drugs or hepatotoxins, including herbal and dietary supplements, plants and mushrooms
- Heritable disorders causing impaired glucuronidation (eg, Gilbert's Syndrome, Crigler-Najjar syndrome) and drugs that inhibit bilirubin glucuronidation (eg, indinavir, atazanavir)
- Alpha-one antitrypsin deficiency
- Alcoholic hepatitis
- Autoimmune hepatitis
- Wilson's disease and hemochromatosis
- Nonalcoholic Fatty Liver Disease including Steatohepatitis
- Non-hepatic causes (eg, rhabdomylosis, hemolysis)

Amgen Investigational Product and other protocol-required therapies, as appropriate, should be withheld pending investigation into alternative causes of Drug Induced Liver Injury (DILI). If Investigational Product(s) is/are withheld, the subject is to be followed for possible DILI. Rechallenge may be considered if an alternative cause for impaired liver tests (ALT, AST, ALP) and/or elevated TBIL, is discovered and the laboratory abnormalities resolve to normal or baseline. Permanent discontinuation of Investigational Product is recommended if all of the following apply:

- TBL > 2 x ULN or INR > 1.5
- AND increased AST or ALT from the relevant baseline value as specified below:

Baseline AST or ALT value	AST or ALT elevation
< ULN	> 3 x ULN

- AND no other cause for the combination of the above laboratory abnormalities is immediately apparent (eg, hepatobiliary tract disease, viral hepatitis, right-sided heart failure, hypotension or any cause of hypoxia to the liver causing ischemia, etc.)

Conditional withholding of investigational medicinal product or other protocol-required therapies is recommended if all of the following apply:

- Elevation of either AST or ALT according to the following schedule:

Baseline AST or ALT value	AST or ALT elevation
Any	> 8 x ULN at any time
Any	> 5 x ULN but < 8 x ULN for $\geq$ 2 weeks
Any	> 5 x ULN but < 8 x ULN and unable to adhere to enhanced monitoring schedule
Any	> 3 x ULN with clinical signs or symptoms that are consistent with hepatitis (such as right upper quadrant pain/tenderness, fever, nausea, vomiting, and jaundice).

- OR: TBIL > 3 x ULN at any time
- OR: ALP > 8 x ULN at any time

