### Drug-induced Liver Injury Reporting & Additional Assessments

#### Reporting

To facilitate appropriate monitoring for signals of DILI, cases of concurrent AST or ALT and TBL and/or INR elevation according to the criteria specified in Section 6.3 require the following:

The event is to be reported to Amgen as a serious adverse event within 24 hours of discovery or notification of the event (ie, before additional etiologic investigations have been concluded)

The appropriate eCRF (eg, Event eCRF) that captures information necessary to facilitate the evaluation of treatment-emergent liver abnormalities is to be completed and sent to the Amgen.

Other events of hepatotoxicity and potential DILI are to be reported as serious adverse events if they meet the criteria for a serious adverse event defined in Section 9.2.1.2.

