**5.3 Study Points of Reference**

**Baseline**

Unless otherwise stated, baseline will be defined as the last assessment taken prior to the first AMG 334 administration (ie, Day 1 pre-dose or Screening if Day 1 pre-dose is not available) of the ITP. For subjects continuing treatment in an OEP after completion of the ITP, their baseline will be the same as the ITP.

For ECG and Neurological Evaluation, the entire set of data from the Day 1 visit will be used as baseline. If the data is missing on Day 1, the entire set of data from the Screening visit will be used as baseline.

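### The permanent-stop rule for liver injury (Protocol 6.3.1) has no AST/ALT row for a baseline at or above ULN, although criterion 214 admits baselines up to just under 2 x ULN

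*Protocol*

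**What the plan says.** **Permanent stop (Protocol 6.3.1).** "Permanent discontinuation of Investigational Product is recommended if all of the following apply": TBL above 2 x ULN or INR above 1.5; "increased AST or ALT from the relevant baseline value as specified below"; and no other evident explanation. The table under the second condition has a single row, for a baseline below ULN, with an elevation above 3 x ULN.

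**Conditional withholding (same section).** All four AST/ALT rows carry the baseline entry 'Any':
- above 8 x ULN;
- between 5 and 8 x ULN for two weeks or more;
- between 5 and 8 x ULN in a subject who cannot follow the closer monitoring;
- "> 3 x ULN with clinical signs or symptoms that are consistent with hepatitis".

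TBIL above 3 x ULN and ALP above 8 x ULN are added as alternatives. INR does not appear.

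**Who may enter.** Criterion 214 in Section 4.2 excludes ALT or AST at or above "2.0 times the upper limit of normal (ULN) for the age range, confirmed by repeated measure". Criterion 106 in Section 4.1 leaves other laboratory findings to the judgement of the investigator and the medical monitor. SAP Section 5.3 takes baseline as the "last assessment taken prior to the first AMG 334 administration".

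**Reporting (Protocol Appendix A).** "cases of concurrent AST or ALT and TBL and/or INR elevation according to the criteria specified in Section 6.3 require the following": an SAE report within 24 hours, made before the search for a cause is finished.

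**The concern.** The table asks for a baseline category and then supplies only one. A subject whose AST and ALT both start at or slightly above ULN is eligible, yet has no row to be judged against. The conditional table beside it covers any baseline, so the restriction looks unintended.

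Two things depend on the row: the explicit recommendation to stop for good, and the automatic SAE report, because Appendix A defines its trigger by pointing back to Section 6.3. These subject-level rules carry some weight here. SAP Section 7.1 plans no early stopping rules, and the DMC makes no recommendations about this study.

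**Working it through.** The plan gives no figure to reproduce. The check applies the printed rules to cases.

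**1. Baselines in the gap.** Let b be an enzyme's baseline in multiples of ULN. Criterion 214 admits b < 2.0. The permanent-stop row requires b < 1.0. Admitted without a row: 1.0 <= b < 2.0.

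**2. The rules.** Let x be the on-study value of the same enzyme (all values x ULN, except INR).
- Permanent = (TBL > 2 or INR > 1.5) and (b < 1 and x > 3, for AST or for ALT) and no other cause.
- Conditional = x > 8; or 5 < x < 8 for at least 2 weeks; or 5 < x < 8 and unable to follow the monitoring; or x > 3 with hepatitis signs; or TBL > 3; or ALP > 8.

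If b >= 1 for both enzymes, the permanent rule is false for every x.

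**3. Six constructed patterns.** No other cause, ALP <= 8, both enzymes starting at the stated baseline, and no symptoms or visible jaundice unless stated. Each cell gives permanent / conditional.

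| Pattern | b = 0.9 | b = 1.1 |
|---|---|---|
| A: ALT 4, TBL 2.5 | yes / no | no / no |
| B: ALT 6 for 1 week, monitoring followed, TBL 2.5 | yes / no | no / no |
| C: ALT 4, INR 2.0, TBL 1 | yes / no | no / no |
| D: ALT 4, TBL 3.5 | yes / yes | no / yes |
| E: ALT 9, TBL 2.5 | yes / yes | no / yes |
| F: ALT 4, TBL 2.5, with symptoms or jaundice | yes / yes | no / yes |

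The results at b = 1.0 and b = 1.9 are the same as at b = 1.1.

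**4. A grid.** Baselines 0.8, 1.0, 1.5 and 1.9; x of 3.5, 4.5, 6 and 9; and TBL 2.5, INR 1.6 or TBL 3.5. That is 4 x 4 x 3 = 48 cases, all asymptomatic, under 2 weeks, with monitoring followed and no ALP elevation.
- At b = 0.8 the permanent rule is met in 12 of 12.
- At b = 1.0, 1.5 and 1.9 it is met in 0 of 36.
- Cases meeting neither rule, per raised baseline: x of 3.5, 4.5 or 6 with TBL 2.5 or INR 1.6, so 3 x 2 = 6. Over three baselines, 18 of the 36.
- With 'Any' in the baseline cell, the permanent rule is met in 36 of 36, and the 12 cases at b = 0.8 are unchanged.

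**5. The uncovered band.** Both enzymes at or above ULN at baseline, ALP <= 8 and no hepatitis signs:
- x above 3 up to 5, or above 5 and below 8 for under 2 weeks with monitoring followed;
- together with TBL above 2 up to 3, or INR above 1.5 with TBL at or below 3.

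**6. Mixed baselines.** The row reads AST or ALT. With ALT at 1.1 and AST at 0.9 at baseline, the rule can still be met once AST exceeds 3. It is not met if ALT alone rises to 4 and AST stays at or below 3. Here the gap is partial.

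**7. The SAE trigger.** The permanent rule is the only Section 6.3 criterion that pairs an aminotransferase with TBL or INR. Patterns A to C at a raised baseline meet no numerical criterion in Section 6.3, so on any reading they do not set off the automatic report. D to F meet a conditional criterion. Whether the report is automatic for them depends on whether Appendix A's reference covers all of Section 6.3 or only the paired rule. The pairing in Appendix A's own wording fits the narrower reading better, but does not settle it.

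**The case against.** The strongest reply is that little changes in practice. Section 6.3.1 says, without a baseline limit, that the product should be held while other causes of liver injury are looked into. It also says "Rechallenge may be considered if an alternative cause for impaired liver tests (ALT, AST, ALP) and/or elevated TBIL, is discovered", and adds that the tests must have resolved. With no other cause found, that comes close to a permanent stop. The missing rule is itself only a recommendation, with a judgement built in.

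Appendix A starts close observation above 3 x ULN, with retesting every 24 hours when TBL exceeds 2 x ULN or INR exceeds 1.5. Section 9.1.2 names drug-induced liver injury as an example of a medically important SAE, and SAEs are due within 24 hours. SAP Section 9.6.3 counts suspected Hy's Law cases and AST/ALT above 3 x ULN with no stated baseline restriction. The study enrols about 52 to 60 subjects, and Protocol Section 2.3 lists no hepatic reaction among the identified adverse drug reactions. INR is not a scheduled analyte.

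Most of this stands and sets the severity. It does not remove the gap. The SAE route in Section 9.1.2 is discretionary, whereas Appendix A's report is not. INR is ordered under close observation once an enzyme passes 3 x ULN, so pattern C can arise, and the conditional rule has no INR limb to catch it. A lost table row cannot be fully excluded in machine-read text, but the next condition follows directly and the neighbouring table kept its four rows.

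**Conclusion.** The point holds and is minor. As printed, an enzyme with a baseline at or above ULN cannot satisfy the AST/ALT part of the permanent-stop rule. When both enzymes start there, the band in step 5 meets neither the permanent nor the conditional rule and does not set off the automatic SAE report. What is lost is the explicit permanent-stop recommendation and the automatic report.

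A reader might infer three stronger things that the documents do not support:
- That every subject with a raised baseline is outside the rule. One enzyme below ULN at baseline can still qualify.
- That the automatic report is lost for all liver patterns at a raised baseline. For those meeting a conditional limb, it depends on how the reference to Section 6.3 is read.
- That these subjects are unprotected. General withholding and close observation apply at any baseline.

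The conclusion assumes that the printed table is complete. The six patterns and the grid are constructed, and the documents give no rate of raised baselines, so no patient count follows.

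**What to change.** First confirm in the PDF that no row is missing. Then, in the permanent-discontinuation table of Section 6.3.1, change the baseline cell from '< ULN' to 'Any' and keep '> 3 x ULN'. This matches the conditional table and completes the Appendix A trigger without further edits.

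The cost is one table cell and a notice to sites, with no extra subjects, visits or scheduled blood draws. The change only adds cases to the rule.

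The downside is a smaller relative rise before a stop is recommended: 3 / 1.5 = 2.0-fold at a baseline of 1.5 x ULN, falling towards 3 / 2 = 1.5-fold as the baseline nears 2 x ULN. TBL above 2 x ULN or INR above 1.5, with no other evident cause, would still be required.

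If the sponsor prefers a separate row for baseline at or above ULN, it needs an explicit threshold. Twice baseline would give 2 x 1.1 = 2.2, 2 x 1.5 = 3.0 and 2 x 1.9 = 3.8 x ULN, so above a baseline of 1.5 x ULN it would act later than 3 x ULN. The choice of threshold is a clinical one for the sponsor.
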